10.6.3.1 QuantiFERON-CMV

Quantiferon-CMV (manufactured by QIAGEN), is an in-vitro diagnostic test using a cocktail of human leukocyte antigen class 1-restricted CMV peptide antigens that are associated with CMV infection (pp28, pp50, pp65, IE-1, IE-2, and gB) to stimulate cells in heparinised whole blood via the detection and measurement of IFN- γ production by Enzyme-Linked Immunosorbent Assay (ELISA).

Loss of this immune function (CMV-specific CD8+ responses) may be associated with the development of CMV disease. The intended use of QuantiFERON-CMV is to monitor the level of anti-CMV cell mediated immunity in persons at risk of developing CMV disease. QuantiFERON-CMV is not a test for determining CMV infection and should not be used to exclude CMV infection.

The QuantiFERON-CMV test system uses specialised blood collection tubes, which are used to collect whole blood. Incubation of the blood occurs in the tubes for 16 to 24 hours, after which plasma is harvested and tested for the presence of IFN- γ produced in response to the peptide antigens.

The QuantiFERON-CMV test is performed in two stages.

First, whole blood is collected into each of the three QuantiFERON-CMV blood collection tubes, which include a Nil Control tube, CMV Antigen tube and a Mitogen tube. The CMV Antigen tube is coated with peptides simulating CD8+ specific epitopes of CMV proteins where stimulation of CD8+ T cells in whole blood with the CMV peptides results in the production of IFN- γ in infected individuals. The Nil Control tube is used in the QuantiFERON-CMV test as a negative control. The Mitogen tube is used in the QuantiFERON-CMV test as a positive control, such as when there is doubt as to the individual's immune status and can also serve as a control for correct blood handling and incubation.

Second, the tubes are incubated at 37°C as soon as possible, and within 16 hours of collection. Following a 16 to 24 hour incubation period, the tubes are centrifuged, the plasma is removed and the amount of IFN- γ (IU/ml) in the plasma is measured by ELISA. A robust IFN- γ response in the CMV Antigen tube is indicative of immunity to CMV (11).

10.6.3.2 CMV-ELISPOT

The CMV-ELISPOT test (manufactured by Oxford Immunotec) called T-SPOT[®].CMV, is an in-vitro diagnostic test using CMV antigens pp65 and IE-1 to stimulate cells in peripheral blood mononuclear cells (PBMCs) isolated from whole blood via the detection and measurement of IFN- γ production by enzyme-linked immunospot (ELISPOT) assay.

Loss of this immune function (CMV-specific CD4+ plus CD8+ responses) may be associated with the development of CMV disease. The intended use of CMV-ELISPOT is to monitor the level of anti-CMV cell mediated immunity in persons at risk of developing CMV disease. CMV-ELISPOT is not a test for determining CMV infection and should not be used to exclude CMV infection.

The CMV-ELISPOT test system uses a heparinised blood collection tube to collect whole blood that is then washed to remove any sources of background interfering signal and isolated into PBMCs and tested for the presence of IFN- γ produced in response to the peptide antigens by capturing them directly around the secreting cell, before it is diluted in the supernatant, bound by receptors of adjacent cells or degraded.

Four wells are required for each sample:

1. Nil Control to identify non-specific cell activation
2. Panel CMV-A: CMV-specific antigen, IE-1

3. Panel CMV-B: CMV-specific antigen, pp65
4. Positive Control: Mitogen solution containing phytohaemagglutinin (PHA, a known polyclonal activator2) to confirm PBMC functionality.

The PBMCs are incubated with the antigens to allow stimulation of any sensitised T cells present. IFN- γ is captured by specific antibodies on the membrane, which forms the base of the well, and the PBMCs and other unwanted materials are removed by washing. A second antibody, conjugated to alkaline phosphatase and directed to a different epitope on the cytokine molecule, is added and binds to the cytokine captured on the membrane surface. Any unbound conjugate is removed by washing. A soluble substrate is added to each well; this is cleaved by bound enzyme to form a spot of insoluble precipitate at the site of the reaction. Each spot represents the footprint of an individual IFN- γ secreting T cell, and evaluating the number of spots obtained provides a measurement of the abundance of CMV-sensitive T cells in the peripheral blood.

10.6.3.3 CMV PCR DNA

All saliva, urine and vaginal secretion samples collected from the participants, and all saliva samples collected from the participants' newborns, will be tested for CMV DNA via real-time polymerase chain reaction (rtPCR) with internal controls using automatic molecular processing in the St George's laboratory under the relevant St George's laboratory Standard Operating Procedures. Quantification standards will be used to evaluate the quantitative detection to copies/ml and where necessary the semi-quantitative detection (CT value -cycle threshold) of CMV DNA in clinical samples.

10.6.4 Sample storage

Samples are stored in the St George's research laboratory under relevant Standard Operating Procedures. Samples will be stored in the lab for two years in case they need to be referred to for a patient's clinical care. Any further storage for further research purposes will be anonymous and subject to prior consent. After this point they will be destroyed according to routine practice.

10.6.5. Sample collection and sample storage due to disruption caused by COVID-19 Pandemic

During the COVID-19 outbreak, face-to-face study visits, new recruitment and screening are suspended. Remaining participants will be offered the opportunity to continue with their study participation through the storing of their samples according to their usual study visit time-points at home until it is safe for the study team to collect the samples from the participants. This will involve the participants continuing to perform self-sampling of saliva, urine and vaginal secretions but instead of providing the samples to the research team on the day of the sampling, they will place the samples inside a securely sealed bag and store the sealed bag in the freezer at home. Participants will be provided with written instructions on how to do this and any additional sampling consumables via post. During this period of time it will not be possible to take blood samples or saliva swabs of newborns and so these will be seen as missing data points. For participants who do not agree to the storage of their samples in the freezer, or who lack access to a freezer, they will be withdrawn from the study or resume their study visits normally when it is safe to do so if suitable. Collection of home frozen samples will take place once the situation

has improved and we are able to see participants face-to-face. Participants will be contacted to update them on the changes required to the study due to the COVID-19 outbreak.

10 Safety Events

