9.3 Study Visit Phase

There will be four study visits (Visit 1, Visit 2, Visit 3, and Visit 4) for each participant:

- Visit 1: as soon as possible following screening, aiming up to 16 weeks and 6 days gestational age (early in pregnancy)
- Visit 2: 20 gestational weeks or any time in 2nd trimester from 17 weeks and 0 days gestational age to 26 weeks and 6 days gestational age (mid pregnancy)

- Visit 3: 28 gestational weeks or any time in 3rd trimester from 27 weeks and 0 days gestational age onwards (late in pregnancy)
- Visit 4: from the time of birth to 1 week postnatal age (postpartum period)

The timing for each visit was chosen following a discussion with the obstetric member of the trial management team ([name]) and our PPI group (the South London Maternal and Paediatric Infection & Immunity Patient and Public Involvement group) to strike a balance of coinciding with routine antenatal appointments for the convenience of the participants to promote on-going participation, and capturing samples throughout pregnancy at varying gestational stages. Where a visit is not possible to coincide with routine antenatal (or postnatal) appointments (in particular Visit 1), this will then take place in a clinical setting, and if still not possible, in the participant's home.

9.3.1 Visit 1

At Visit 1, after the participant has signed the written informed consent, the relevant study procedures can be performed in any order, which are:

- Background questionnaire
- Contact questionnaire
- Self-sampling of saliva, urine and vaginal secretions
- Venous blood sampling where consent is obtained

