10.3.1.2 Self-sampling of Saliva, Urine and Vaginal Secretions

At the Visit 1, the study team will explain and provide the participant with the ethically approved, study specific, written instructions on how to perform self-sampling of saliva, urine and vaginal secretions. The study team will collect these samples on the same day of the sampling. Self-sampling of saliva, urine and vaginal secretions will be performed on the day of each visit by the participant, using the written instruction provided without the need for any supervision by the study team, however the participant will be encouraged to seek advice and ask the study team any questions they may have regarding the self-sampling techniques. The participant will be provided with enough self-sampling kits to last them for the whole study period.

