10.6.3 Laboratory procedures

All saliva, urine and vaginal secretion samples collected from the participants will be tested for CMV DNA via polymerase chain reaction (PCR). These tests will be performed in multiple batches and not in 'real-time' within the limitations of sample integrity. All saliva samples collected from the newborns will be tested for CMV DNA PCR in 'real-time'.

For the blood samples, CMV-specific T cell immune responses will be analysed using two commercially available IGRAs; the QuantiFERON-CMV assay and CMV-ELISPOT assay.

The blood samples that will be analysed will take into account several factors; for all participants where CMV shedding is detected, the corresponding blood samples (same participant and same visit number as when shedding was detected) and other blood samples (same participant but at different visit numbers even when shedding does not occur) will be tested. A proportion of participants where CMV shedding is not detected at all will have their blood samples tested, and will take into account the prevalence, sociodemographic details, gestational stages and the source of shedding (saliva, urine and/or vaginal secretions) of the participants that shed.

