11.2 Data collection tool

Case Report Forms will be designed by the CI or a delegated member of the study team. All data will be entered legibly in black ink with a ball-point pen. If the Investigator makes an error, it will be crossed through with a single line in such a way to ensure that the original entry can still be read. The correct entry will then be clearly inserted. The amendment will be initialled and dated by the person making the correction immediately. Overwriting or use of correction fluid will not be permitted.

It is the Investigator's responsibility to ensure the accuracy of all data entered and recorded in the CRFs. The Staff Delegation of Responsibilities Log JRESLOG0004 will identify all trial personnel responsible for data collection, entry, handling and managing the database.

Data will be recorded directly onto the CRF.

An initial entry will be made in the participant's handheld notes describing the participant's involvement in a research study. The front page of the handheld notes will have a sticker placed on it to alert clinical staff to study participation. Any further correspondence between the study team and clinical colleagues will take place by letter.

There are three types of study-specific questionnaires to be completed throughout the study period (background and contact questionnaires at Visit 1, contact questionnaire at Visit 2 and 3, contact and feedback questionnaires at Visit 4). At Visit 1 and 4 which require face to face contact, the questionnaires will be completed electronically on an electronic device (and if not possible on hard copy). For Visit 2 and 3, a link to the contact questionnaire will be emailed out to participants along with a text. If participating women do not have access to a computer, the questionnaire may be mailed to them and a pre-paid envelope provided.

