13.4.3 Secondary endpoint analysis

For each sample type (saliva, urine, vaginal secretions), the percentage of participating women with detectable CMV DNA as measured by quantitative PCR, will be calculated for each study visit (Visit 1, Visit 2, Visit 3, Visit 4), and cumulatively, with 95% CIs.

For each study visit (Visit 1, Visit 2, Visit 3, Visit 4), the percentage of participating women with detectable CMV DNA as measured by PCR, will be calculated for each sample type (saliva, urine, vaginal secretions), and cumulatively, with 95% CIs

CMV shedding will also be assessed quantitatively, as measured by quantitative PCR on the amount of CMV DNA detected, in each sample type and at each study visit, separately and cumulatively, with 95% CIs.

The distributions of sample type, study visit number, detectable shedding and quantity of shedding will be summarised graphically and described using means and medians, as appropriate.

Factors associated with CMV shedding as a binary outcome (detectable shedding versus no detectable shedding) will be investigated using multivariable mixed effects models. Potential risk factors will be those assessed using the study sociodemographic questionnaire at Visit 1 and risk factor questionnaires at all visits (these variables may be time-varying) – these will include ethnicity, age, number of children, parental occupation, age of child(ren), and type of handling with child(ren)'s urine and saliva.

Acceptability of the study design and procedures will be analysed descriptively, for example by calculating mean scores derived from satisfaction scales. We will also investigate factors associated with satisfaction, defined as a binary variable, using logistic regression. We will summarise free text comments made through the feedback questionnaire.

The percentage of eligible women who consent to participate, and the percentage of participants who complete the study (provide urine, saliva and vaginal secretion samples and questionnaire data at all four study visits, with or without blood and newborn saliva samples), will be calculated.

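### Home-frozen COVID-19 samples are analysed like all others, although they come essentially from Visits 2 to 4, so storage is partly confounded with gestational stage

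*Combined protocol and SAP*

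**What the plan says.** Under normal conduct, section 10.3.1.2 states: "The study team will collect these samples on the same day of the sampling". Samples then go to the research laboratory and are stored under its procedures (sections 10.6.2 on labelling and transport, and 10.6.4). Maternal PCR is run in batches "within the limitations of sample integrity" (section 10.6.3).

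Section 10.6.5, the only change that Appendix 1 lists for version 3.0, says that during the outbreak "face-to-face study visits, new recruitment and screening are suspended". Remaining participants may continue by "storing of their samples according to their usual study visit time-points at home until it is safe for the study team to collect". After each self-sampling, "they will place the samples inside a securely sealed bag and store the sealed bag in the freezer at home". The section refers to written instructions for participants, but itself gives no freezer temperature, maximum duration or acceptance rule.

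Two other places fix which visits can be affected. Section 9.3 says: "At Visit 1, after the participant has signed the written informed consent, the relevant study procedures can be performed in any order". Section 11.2 groups the visits by contact: "At Visit 1 and 4 which require face to face contact".

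On analysis:
- Section 13.4.2 counts a woman as a shedder if any pregnancy sample is positive.
- Section 13.4.3 gives percentages and quantities by fluid and by visit. Its mixed effects model for risk factors names no storage or period term.
- Section 13.4.5 has one extra analysis, in women with samples at all three time points. That analysis keeps home-frozen samples.
- Section 4.2 makes comparison of prevalence and quantity between gestational stages a secondary objective, and the synopsis expresses it as fold-differences.

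**The concern.** Handling changed for some samples and the analysis did not follow. The change does not fall evenly over pregnancy: Visit 1 has essentially no home-frozen samples, while Visits 2 to 4 have some. If home storage lowers detection or copies/ml, the planned by-visit estimates would show a decline with gestation that is partly an artefact of storage. Quantity is exposed even where a sample stays positive. The primary endpoint could also be pulled down, and section 13.2 says that this prevalence is a key input for sizing future studies.

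**Working it through.** **1. Which visits can be home-frozen.** A woman consents at Visit 1 and then gives her first samples (section 9.3). Visit 1 is face to face (section 11.2). Both new recruitment and face-to-face visits were suspended (section 10.6.5). A remaining participant has therefore already entered Visit 1. The only exception would be a woman who consented just before the suspension without giving samples, which the documents do not describe.

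**2. The plan's own precision (section 13.3.1).** With p = 0.30 and N = 200, the half-width is 1.96 × √(0.30 × 0.70 / 200) = 6.35 points. This agrees with the stated ±6% after rounding. It belongs to the cumulative endpoint (any fluid, any point in pregnancy), not to a single visit.

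**3. Share frozen (assumed).** Take even recruitment of 200 women over 12 months, ending at the suspension, with Visit 1 at 14 weeks. The rate is 200 / 52.18 = 3.83 women per week.
- Visit 2 (20 weeks) outstanding: 3.83 × 6 = 23 women, about 12%.
- Visit 3 (28 weeks) outstanding: 3.83 × 14 = 54 women, 27%.

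Varying Visit 1 from 12 to 16.9 weeks gives 6-15% at Visit 2 and 21-31% at Visit 3. As a heavier case I also take 25% and 50%.

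**4. Effect on the gestational comparison.** Let f3 be the share frozen at Visit 3 and L the relative loss of detection (assumed). With equal true shedding at both visits, the apparent Visit 3:Visit 1 ratio is 1 − f3 × L.

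| L | f3 = 27% | f3 = 50% |
|---|---|---|
| 0 | 1.00 | 1.00 |
| 10% | 0.973 | 0.95 |
| 20% | 0.946 | 0.90 |
| 30% | 0.919 | 0.85 |

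**5. Effect on the primary endpoint.** Assume three independent pregnancy visits with equal per-visit shedding p1 that accumulate to 30%: p1 = 1 − 0.70^(1/3) = 11.2%. Let q = p1(1 − L), and let women frozen at Visit 2 also be frozen at Visit 3. Then:

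prevalence = 1 − [f2(1 − p1)(1 − q)² + (f3 − f2)(1 − p1)²(1 − q) + (1 − f3) × 0.70].

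- f2 = 12%, f3 = 27%: 29.7% at L = 10%, 29.0% at L = 30%.
- f2 = 25%, f3 = 50%: 29.3% at L = 10%, 28.0% at L = 30%.
- Even with L = 50% in the heavier case: 26.6%, a fall of 3.4 points against a half-width of 6.35.

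**6. Can storage and visit be separated?** Yes, if storage is recorded. In a linear model with visit and storage terms, treating observations as independent with equal numbers per visit, the variance of the Visit 3 v Visit 1 contrast is multiplied by 1 + f3² / (2 × Σ f(1 − f)), summed over Visits 2 and 3.
- 12%/27%: 1 + 0.0729 / (2 × 0.3027) = 1.12.
- 25%/50%: 1 + 0.25 / (2 × 0.4375) = 1.29.

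**7. Would dropping frozen samples do for the primary endpoint?** No. In the 25%/50% case with no storage loss at all, deleting those samples leaves 25% of women with Visit 1 only and 25% with Visits 1 and 2. Prevalence becomes 1 − (0.25 × 0.888 + 0.25 × 0.788 + 0.50 × 0.700) = 23.1%. The fall of 6.9 points comes only from fewer sampling occasions, and exceeds the storage bias in every scenario above.

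**The case against.** The strongest case against is that nothing shows harm. No section says that home freezing reduces detection or quantity, and if the loss is zero there is no bias. Samples collected on the day also wait in storage for batch PCR, so the contrast is home freezer against laboratory storage, not stored against fresh. The primary endpoint is diluted, because any positive fluid at any pregnancy visit counts and Visit 1 is unaffected. This is a feasibility study whose by-visit analysis consists of percentages with confidence intervals, with no formal test between stages specified. The sampling date is written on every sample (section 10.6.2 on labelling), so samples taken during the suspension can largely be identified afterwards.

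All of this stands, and it limits the size of the point. It does not remove it: gestational-stage comparison is a stated objective, and the plan has no step that would show whether storage matters.

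Three stronger readings are tempting. First, that storage and gestation cannot be separated: women seen before the suspension also gave samples collected on the day at Visits 2 to 4, so the overlap is partial (step 6). Second, that a visit-level prevalence of 30% would fall by an amount to be judged against ±6 points: both figures in section 13.3.1 refer to the cumulative endpoint. Third, that the plan prescribes pooling: no sentence says so, and pooling follows only from silence.

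**Conclusion.** The point holds as a gap in the analysis plan of modest size. Home-frozen samples fall essentially at Visits 2 to 4, and section 13.4 treats them like the rest, so storage is partly confounded with gestational stage. Under the assumed 27-50% frozen at Visit 3 and 10-30% relative loss, a true ratio of 1.00 would appear as about 0.97 to 0.85. The exposure is mainly in the by-visit and gestational-stage comparisons of prevalence and quantity. The primary prevalence would move from 30% to about 29.7-28.0%, within the planned half-width, although the confidence interval does not reflect a bias of this kind. Visit 4 is postpartum and lies outside the primary endpoint. The frozen shares, the loss, and the equal and independent shedding across visits are all assumptions. A reader might infer that the primary result is seriously compromised or that home freezing is known to degrade samples; the documents support neither.

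**What to change.** - For each sample, record storage type (home-frozen or collected on the day) and days from sampling to laboratory receipt.
- In section 13.4.5, pre-specify by-visit prevalence and quantity with and without home-frozen samples, and by storage type within the same visit.
- Make the gestational-stage comparison with a model that has both visit and storage terms. Adding storage to the risk-factor model alone would leave the separate by-visit percentages unadjusted.
- For the primary endpoint, do not delete home-frozen samples (step 7). Repeat it in women whose pregnancy samples were all collected on the day.

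The cost is two data fields per sample and a re-run of planned analyses. No visit or procedure changes. Precision at later visits is lower: the variance of the Visit 3 v Visit 1 contrast rises about 1.12- to 1.29-fold in the cases shown. The storage contrast also remains tied to the pandemic period, so a difference by storage could reflect changed exposure or behaviour. The report should say so.

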10.1 Definitions

Adverse Event (AE)—any untoward medical occurrence in a participant whether it is considered to be related to the intervention or not, that includes a clinical sign, symptom, or condition and /or an observation of a near incident. (This does not include pre-existing conditions recorded as such at baseline)

Serious Adverse Event (SAE)—any Adverse Event or untoward medical occurrence in a trial participant that can be wholly or partly to the intervention, which resulted in any of the following:

- Results in death; or
- Is life-threatening (places the participant, in the view of the Investigator, at immediate risk of death)
- Requires hospitalisation or prolongation of existing hospitalisation (hospitalisation is defined as an inpatient admission, regardless of length of stay; even if it is a precautionary measure for observation; including hospitalisation for an elective procedure, for a pre-existing condition)
- Results in persistent or significant disability or incapacity (substantial disruption of one's ability to conduct normal life functions)
- Consists of a congenital anomaly or birth defect (in offspring of participants regardless of time of diagnosis).
- Or is another important medical condition

Important medical events that may not be immediately life-threatening or result in death or hospitalisation but may jeopardise the participant or may require intervention to prevent one of the outcomes listed in the definition of serious will also be considered serious.

